7 STUDY TREATMENTS

7.1 Description of investigational medicinal products

Only the following study drug will be supplied by UCB for N01349:

- BRV 10mg/mL iv solution in a 5mL vial.

For subjects who are switched to BRV oral solution in the BRV Extension Period, the following will be supplied by UCB:

- BRV oral solution, at concentrations of 10mg/mL, will be supplied in 300mL glass bottles.

Refer to the IMP Handling Manual for further details on the handling of BRV.

There is no placebo or reference product.

After the completion of the study, BRV treatment per SOC may be continued as prescribed but will not be provided by the Sponsor.

7.2 Treatments to be administered

Subjects in the Exploratory Cohort will be dosed during the Evaluation Period with BRV (0.5mg/kg bid) according to the sites standard procedures. Treatment with AEDs per SOC (first-line, second-line, or subsequent treatment) will continue in parallel with BRV treatment.

For subjects who enter the Confirmatory Cohorts, the dosing of BRV (1mg/kg bid [2mg/kg/day]) has been determined based on the PK findings of the Exploratory Cohort. The DMC will continue to monitor the PK and safety of the subjects and dosing may be adjusted as new data are available. Administration of BRV is proposed as approximately 15-minute iv infusions.

Treatment with previous AEDs (PB, MDZ, PHT, LEV [\leq 60mg/kg/day], or LDC) during the Evaluation Period is permitted to continue if the subject is on a stable dose from 1 hour prior to initiation of the BRV treatment.

Subjects can switch from iv to oral BRV at any time during the BRV Extension Period.

For subjects who are switched to BRV oral solution, the dose will be measured using the appropriate syringes (1mL, 3mL or 10mL) with an adaptor able to fit all the bottle sizes. Oral solution should not be mixed with other liquids prior to administration.

7.3 Packaging

Brivaracetam (sterile solution for iv infusion and oral solution) is manufactured, packaged, and labeled according to Good Manufacturing Practice (GMP) guidelines and applicable laws or regulations. Brivaracetam is suitably packaged in such a way as to be protected from deterioration during transport and storage.

Brivaracetam sterile solution for iv infusion 10mg/mL will be packaged in 5ml vials.

Brivaracetam 10mg/mL oral solution will be packaged in 300mL type-III amber glass bottles with child-resistant tamper evident polypropylene screw closures. Syringes of 1mL, 3mL or 10mL will be provided with an adaptor able to fit all the bottle sizes.

Other AED treatments will be used for this study and will not be provided or covered by the Sponsor.

7.4 Labeling

Clinical drug supplies will be labeled in accordance with the current International Council on Harmonisation (ICH) guidelines on Good Clinical Practice (GCP) and GMP and will include any locally required statements. If necessary, labels will be translated into the local language.

7.5 Handling and storage requirements

The Investigator (or pharmacist/designee) is responsible for the safe and proper storage of BRV at the site. Brivaracetam stored by the Investigator is to be kept in a secured area with limited access according to the storage conditions mentioned on the label.

Appropriate storage conditions must be ensured either by controlling the temperature (eg, room, refrigeration unit) or by completing a temperature log in accordance with local requirements on a regular basis (eg, once per working day), showing actual minimum/maximum temperatures reached over the time interval.

Additional information pertaining to the handling of BRV, a Schedule V drug, is provided in the IMP Handling Manual.

In case an out-of-range temperature is noted, it must be immediately reported as per instructions contained in the IMP Handling Manual.

The Investigator (or designee) will instruct the subject to store the IMP following the instructions on the label.

7.6 Drug accountability

A Drug Accountability form will be used to record BRV dispensing and return information on a by-subject basis and will serve as source documentation during the course of the study. Details of any BRV lost, damaged (due to breakage or wastage), not used, partially used, disposed of at the study site, or returned to the Sponsor or designee must also be recorded on the appropriate forms. All supplies and pharmacy documentation must be made available throughout the study for UCB (or designee) to review.

The Investigator (or designee) is responsible for retaining all used, unused, and partially used containers/ bottles of BRV until returned or destroyed.

The Investigator may assign some of the Investigator's duties for drug accountability at the study site to an appropriate pharmacist/designee.

The Investigator must ensure that BRV is used only in accordance with the protocol.

Periodically, and/or after completion of the clinical phase of the study, all used (including empty containers)/partially used, unused, damaged and/or expired IMP containers/ bottles must be reconciled and either destroyed at the site according to local laws, regulations, and UCB Standard Operating Procedures (SOPs), or returned to UCB (or designee). Investigational medicinal product intended for the study cannot be used for any other purpose than that described in this protocol.

7.7 Procedures for monitoring subject compliance

After each iv BRV administration, empty/used BRV containers must be kept.

All unused IMP and empty IMP containers/bottles must be accounted for or returned to the site. For subjects treated at home during the BRV Extension Period, parent(s) or legal representative(s) should be advised to return all unused IMP and empty IMP bottles to the site. Drug accountability must be done in the presence of the subject's parent(s) or legal representative(s) and site staff to obtain explanations regarding discrepancies in compliance with the dosing regimen. Drug accountability must be recorded on the Drug Accountability form.

Site personnel who are administering iv BRV will record information about all doses administered, including the target dose, actual dose administered, and the dates and times of initiation and completion of each iv administration. If the actual dose is less or more than the target dose, the reason a partial or excessive dose was administered will be recorded.

Intravenous BRV solution will be administered under supervision of the Investigator or his/her designee. The noninjected volume will be recorded in the eCRF. Compliance with the recommended duration of the iv administration will also be assessed by recording the start time and the stop time in the eCRF.

Noncompliance will be recorded for subjects who are administered <75% or >125% of the planned BRV dose. If, in the Investigator's opinion, there is persistent noncompliance with the subject's BRV administration, the Sponsor, in conjunction with the Investigator, will make a decision as to whether the subject should be withdrawn from the study.

7.8 Concomitant treatments and medications

7.8.1 Permitted concomitant treatments (medications and therapies)

Concomitant treatment with non-AEDs is permitted for the Exploratory and Confirmatory Cohort(s) at any time throughout the study.

For the Exploratory Cohort, concomitant treatment with AEDs is permitted at any time.

For the Confirmatory Cohorts, concomitant treatment with AEDs is permitted to continue in parallel with BRV treatment if subjects are on a stable dose from 1 hour prior to initiation of BRV treatment. Changes to concomitant AEDs are permitted from 3 hours onward following first BRV administration.

7.8.2 Prohibited concomitant treatments (medications and therapies)

For the Confirmatory Cohorts, subjects will not be permitted to change concomitant treatment for neonatal seizures for the first 3 hours after the first BRV administration.

The initiation of LEV treatment after the first time BRV is introduced is prohibited throughout the study for the Confirmatory Cohorts.

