Rescue medication should be given if the following occurs:

- There is no improvement in seizure burden within the first 3 hours after administration of BRV.
- Seizure burden is unacceptable to the Investigator, in which case rescue medication can be given earlier at any time, but ideally not in the first 3 hours after the initial administration of BRV.

Subjects in the Confirmatory Cohorts are allowed to switch over from BRV to another AED (eg, MDZ or PHT), if needed. Subjects discontinuing BRV treatment during the Evaluation Period should start the Down-Titration Period while completing the Evaluation Period in parallel for the full 96 hours. In this case, subjects will complete all study assessments, except the collection of blood microsamples for the determination of BRV plasma concentrations. Ideally, changing or adding a new treatment should not occur during the first 3 hours after the initial administration of BRV. Subjects who are switched from BRV to another AED will not be eligible to participate either in the BRV Extension Period or the long-term study.

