6.3 Withdrawal criteria

Parent(s) or legal representative(s) are free to withdraw the subject from the study at any time, without prejudice to continued care.

Subjects **must** be withdrawn from the study if any of the following occur:

1. The Sponsor or a regulatory agency requests withdrawal of the subject.
2. Parent(s) or legal representative(s) withdraw their consent for the subject to participate.
3. Subject is treated with prohibited concomitant medications as defined in this protocol.
- 4a. Subject has direct (conjugated) bilirubin levels $>2\text{mg/dL}$.
5. Subject requires phototherapy or exchange transfusion due to elevation of total bilirubin.
- 6a. Subject has AST, ALT or ALP values $3\times$ ULN, with the following exception:

For subjects with perinatal asphyxia, elevation of AST, ALT or ALP $<5\times$ ULN is acceptable for continuation in the study, if initial and peak elevation of LFTs occurs within 5 days after birth, and if the time course of LFT elevation is compatible with hepatic injury due to perinatal asphyxia (ie, peak LFT elevation within a few days after birth, and subsequent normalization until up to day 14 after birth).

In case AST, ALT or ALP elevation $\geq 5\times$ ULN occurs within 5 days after birth, study drug must be discontinued and LFTs retested within 24 hours. If AST, ALT and ALP are confirmed to be $<5\times$ ULN, the subject may restart study drug after consultation with and approval by the Medical Monitor.

The determination of ULN will be based on the subject's GA and the site's normal range values for the respective GA.

Subjects **may** be withdrawn from the study if any of the following events occur:

- 7a. Subject experiences prolongation of seizure duration, a worsening of seizure burden, or emergence of new seizure type considered by the Investigator to require intervention.
8. Investigator may withdraw subject due to any medical condition, based on clinical judgment and discretion.
- 9a. Subject has AST, ALT or ALP values between $>2\times$ and $\leq 3\times$ ULN, with the following exception:

For subjects with perinatal asphyxia, elevation of AST, ALT or ALP <5 x ULN is acceptable for continuation in the study, if initial and peak LFT elevation occurs within 5 days after birth, and if the time course of LFT elevation is compatible with hepatic injury due to perinatal asphyxia (ie, peak LFT elevation within a few days after birth, and subsequent normalization until up to day 14 after birth).

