7.8.3 Rescue medication

Any treatment initiation with a new AED, or any increase of dose or frequency of an existing concomitant AED for the treatment of seizures during the Evaluation Period is considered rescue treatment. Rescue medication can be given at any time if considered necessary by the Investigator.

However, during the Evaluation Period rescue medication should not be administered – if possible – in the following time frames:

- During the first 3 hours after the initial dose of BRV for the Confirmatory Cohorts. If this occurs, subjects will be considered BRV nonresponders for the evaluation of the main efficacy variable.

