8.2.2 Evaluation Period

The first administration of BRV marks the starting point of the Evaluation Period.

Up to 8 iv doses of BRV (1mg/kg bid) will be administered as an approximately 15-minute infusion during the 96-hour BRV Evaluation Period. The AED treatment initiated prior to first

administration of BRV can be continued if the subject is on a stable dose for at least 1 hour at the time the first BRV infusion is initiated.

If subjects do not benefit from BRV treatment after 96 hours of BRV administration, BRV administration will be stopped and replaced by another AED; however, the subjects' participation in the study will continue.

If subjects in the Confirmatory Cohort receive <8 BRV doses, those subjects are allowed to continue study participation and complete study assessments per [Table 5–2](#) with the exception of PK blood sampling. Those subjects should start the Down-Titration Period while completing the Evaluation Period in parallel for the full 96 hours.

After the enrollment of subjects, the weight of the subject will be measured and BRV will be given.

The following assessments will be performed after BRV administration:

- Vital signs (blood pressure, heart rate, respiratory rate [including apneas], oxygen saturation [pulse oximetry], and body temperature; at 0, 3, 6, 9, 12, 15, 18, 21, 24, 48, 72, and 96 hours)
- Physical and neurological examination (Sarnat scale for subjects with HIE; physical examination will include a check for the presence of skin rash and skin hypersensitivity [at 24, 48, 72, and 96 hours])
- Primary cause of seizure (HIE, hemorrhage, or infarction; CNS malformations; CNS infections; undetermined causes [at 96 hours])
- N-PASS and EEG parameters for the assessment of sedation (at 96 hours)
- Body weight (optional [at 24, 48, 72 and 96 hours]; dosage of BRV during the Evaluation Period will be based on the subject's weight measured prior to the start of the first BRV administration. However, dosage calculation can be adjusted to a more recent weight measurement, upon discretion of the Investigator, if weight is measured during the Evaluation Period)
- Video-EEG
- Heart rate monitoring
- Up to 6 PK samples (30 to 60 minutes, 2 to 4 hours, and 8 to 12 hours after the start of the most recent BRV infusion; the same timepoints apply to the first day and 1 of the 3 following days of the 96-hour Evaluation Period).
- Collection of AED PK sample 3 hours after the start of the initial BRV administration

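### A baby rescued within 3 h is called a nonresponder but can still fall out of the VEEG-based denominator, and the instructions on early rescue disagree

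*Protocol*

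**What the plan says.** **Instructions to sites (Confirmatory Cohorts).**
- Protocol 7.8.2, on prohibited treatments: "subjects will not be permitted to change concomitant treatment for neonatal seizures for the first 3 hours after the first BRV administration". It adds: "The initiation of LEV treatment after the first time BRV is introduced is prohibited throughout the study for the Confirmatory Cohorts".
- Protocol 7.8.1 agrees: "Changes to concomitant AEDs are permitted from 3 hours onward following first BRV administration".
- Protocol 6.3 item 3, one of the mandatory withdrawal criteria: "Subject is treated with prohibited concomitant medications as defined in this protocol".
- Protocol 7.8.3 defines rescue as starting any new AED, or raising the dose or frequency of a current one, to treat seizures in the Evaluation Period. It says: "Rescue medication can be given at any time if considered necessary by the Investigator". It asks sites to avoid the first 3 h if they can.
- Protocol 5.1.2 is equally soft: "rescue medication can be given earlier at any time, but ideally not in the first 3 hours after the initial administration of BRV".
- Protocol 8.2.2, on babies who receive fewer than 8 BRV doses: "those subjects are allowed to continue study participation and complete study assessments". Protocol 5.1.2 has babies who stop BRV complete the full 96 h.

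**Outcome.** For rescue in the first 3 h, Protocol 7.8.3 states: "If this occurs, subjects will be considered BRV nonresponders for the evaluation of the main efficacy variable". Protocol 10.1, 13.5.1 and 13.7 and SAP 8.1.1 say the same in substance.

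**Denominator.** SAP 8.2.1 divides by the FAS subjects of the Confirmatory Cohorts. SAP 3.6.2 and Protocol 13.1 admit a dosed subject to the FAS only with at least 2 h of interpretable VEEG from Baseline and the first 3 h after dosing. Neither mentions rescue.

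**Use.** Protocol 13.5.1 compares the 95% CI of the responder rate, all Confirmatory Cohorts combined, with the historical rate.

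**The concern.** The nonresponder rule fixes a baby's outcome. It does not put the baby in the analysis set. A baby who does badly soon after the first dose may be rescued and then have the recording cut short or become unreadable. The plan says that baby failed, but the denominator can leave the baby out. Every loss of this kind removes a failure, so the error runs in one direction, towards BRV.

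The site instructions add to this. One section forbids AED changes in hours 0 to 3, another allows them on the Investigator's judgement, and a mandatory withdrawal criterion refers to prohibited medication without exempting rescue. Two sites could handle the same baby differently, and a site that withdraws the baby also ends the recording on which FAS entry depends.

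**Working it through.** **1. Does any text keep the baby in the denominator?** No.
- SAP 8.1.1 assigns outcome status, not set membership.
- SAP 4.2.3 does not help. Its rescue clause covers more than one dose after the first 3 h, and its switch clause covers switches before the Evaluation Period.
- SAP 8.2.3 presupposes that early-rescued babies are in the FAS, since it removes them from it. It does not place them there.

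**2. When is a baby lost?** Baseline VEEG lasts up to 1 h, or up to 30 min in status epilepticus (Protocol 8.2.1.1). The 2 h minimum is workable only if Baseline and post-dose recording are added together, which is an assumption. The post-dose VEEG then needed is:
- intermittent seizures: 2 − 1 = 1 h;
- status epilepticus: 2 − 0.5 = 1.5 h.

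A baby rescued early whose VEEG continues past that point stays in the FAS as a nonresponder. The loss needs usable recording to stop sooner, for whatever reason.

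**3. Direction.** With r responders among n subjects, the exact (Clopper-Pearson) lower limit is the 2.5% quantile of Beta(r, n − r + 1). Removing a nonresponder lowers the second parameter by 1, so the limit rises. The rate r/n rises as well.

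**4. Size per baby.** The plan has no sample-size calculation and states no CI method, so it offers no figure to reproduce. Inputs: n = 36 (3 × 12, Protocol 13.9); one early-rescued baby lost; exact 95% CI and responder counts assumed.

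| Responders | Rate of 36 | Rate of 35 | Lower limit, 36 | Lower limit, 35 | Rise (points) |
|---|---|---|---|---|---|
| 6 | 16.7% | 17.1% | 6.4% | 6.6% | 0.2 |
| 12 | 33.3% | 34.3% | 18.6% | 19.1% | 0.6 |
| 18 | 50.0% | 51.4% | 32.9% | 34.0% | 1.1 |
| 24 | 66.7% | 68.6% | 49.0% | 50.7% | 1.7 |

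Rises are taken from unrounded limits. If two babies were lost (assumed), 12 responders would give 12/34 = 35.3% with a lower limit of 19.7%.

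**5. Effect on the conclusion.** With one baby lost and 12 responders, the lower-limit comparison in Protocol 13.5.1 changes only if the historical rate lies between 18.6% and 19.1%.

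**6. Can SAP 8.2.3 reveal it?** Take 12 responders and one early-rescued baby. If the baby is in the FAS, the sensitivity denominator is 36 − 1 = 35. If not, it is 35 − 0 = 35. The result is 12/35 = 34.3% either way.

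**The case against.** **The plan means to keep these babies.** Protocol 5.1.2 foresees an early AED change, discourages it, and keeps babies who stop BRV under assessment for 96 h. SAP 5.2 counts FAS subjects with a prohibited-medication deviation. This stands. A reader might infer that 6.3 item 3 requires withdrawal of every baby rescued early. The documents do not support that: item 3 does not mention rescue or AED changes, and for drugs other than LEV the link rests on taking the heading of 7.8.2 as the definition of prohibited medication. What remains is inconsistent wording that permits such a reading.

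**LEV.** A reader might also infer a flat contradiction, because LEV is banned after BRV starts yet fits the definition of rescue. A ban on a named drug most naturally prevails over a general permission, and the switch examples in 5.1.2 are MDZ and PHT. If LEV is started anyway, nonresponder status and withdrawal can both apply. The remaining defect is that 7.8.3 does not carve LEV out.

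**The loss is narrow.** It needs early rescue together with a short recording, and Protocol 5.1 and 7.8.3 discourage both. The endpoint is secondary, the historical comparison is called descriptive, and SAP 4.5 plans no tests. All true, and this limits the weight of the point. Protocol 13.5.1 still states a CI rule for calling BRV efficacious.

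**Restoring only known failures is itself one-sided.** If rescued babies return whatever their VEEG while unrescued babies with the same gap stay out, inclusion depends on outcome. This is correct, and the fix has to deal with it.

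**Conclusion.** The point holds in a limited form. The plan's nonresponder rule for early rescue is not carried into its denominator, so following the SAP as written can drop a known failure. The bias is one-sided, and the planned sensitivity analysis cannot show it. The instructions for hours 0 to 3 are inconsistent, but they do not amount to a clear order to withdraw rescued babies.

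The effect is about 0.2 to 1.7 points on the lower limit for each baby lost from 36. This rests on assumed responder counts, an exact interval, and the pooled reading of the 2 h VEEG rule. The number of babies affected is unknown and probably low, so a changed conclusion under 13.5.1 is unlikely. The correction is worth making because it is cheap and carries out what the plan already says.

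**What to change.** **SAP 8.2.1 (main change).** Define the main denominator as the Confirmatory FAS plus every other dosed Confirmatory subject with rescue, or with an AED start, increase or switch, in the first 3 h. Count these subjects as nonresponders whatever post-dose VEEG is available.

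**Sensitivity analysis.** Add one on all dosed Confirmatory subjects, with unrescued babies who lack evaluable VEEG also counted as nonresponders. Inclusion then no longer depends on outcome.

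**SAP 3.6.2 and Protocol 13.1.** The 2 h minimum does not fit a Baseline of up to 1 h. This is a separate defect, best corrected at the same time by stating the VEEG required in each period.

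**Next protocol amendment.** In 7.8.2 and 6.3 item 3, state that rescue given on the Investigator's judgement under 7.8.3 does not trigger withdrawal and that VEEG continues. In 7.8.3, state that LEV may not be used as rescue.

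**Cost.** The SAP part is a few sentences and one extra table, needs no new data, and need not wait for the protocol. The protocol part needs sponsor, ethics committee and, where required, regulatory approval (Protocol 14.5), so it can go with the next amendment. The price is a slightly lower, conservative responder rate.

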7.8.3 Rescue medication

Any treatment initiation with a new AED, or any increase of dose or frequency of an existing concomitant AED for the treatment of seizures during the Evaluation Period is considered rescue treatment. Rescue medication can be given at any time if considered necessary by the Investigator.

However, during the Evaluation Period rescue medication should not be administered – if possible – in the following time frames:

- During the first 3 hours after the initial dose of BRV for the Confirmatory Cohorts. If this occurs, subjects will be considered BRV nonresponders for the evaluation of the main efficacy variable.

